6.6 Dose Selection and Modification

Physician discretion may be used if monitoring or dose modification outside of the guidelines is considered necessary.

If participants vomit after taking their dose of peposertib and/or capecitabine, they should be given an antiemetic but the dose(s) will not be replaced. Prophylactic antiemetics should then be considered prior to subsequent doses of peposertib and/or capecitabine. Any change from dosing schedule, dose interruptions, or dose reductions should be recorded in the eCRF.

In general, each participant will stay on the peposertib, and capecitabine dose level assigned in the study unless treatment needs to be interrupted, modified or stopped. If peposertib dosing interruptions are necessary, the SMC may decide to start the next cohort at a lower dose level or at a lower dosing intensity (e.g. three times weekly or twice weekly).

If 1 study intervention must be withheld, that study intervention's dose should be skipped rather than delayed, and the other study intervention (capecitabine or peposertib) should be given alone.

If hemoglobin is < 8 g/dL then appropriate measures according to standard clinical practice must be taken prior to any further dose administration.

The SMC will be responsible for dose escalation decisions and will provide input into the selection of a RP2D. Details of SMC decision making processes are provided in [Appendix 2](#). The DLT definition is provided in Section [6.6.1](#).

6.6.1 Definition of Dose Limiting Toxicity

A DLT is defined as any of the following TEAEs considered possibly related to peposertib and/or capecitabine and/or RT by the Investigator and/or the Sponsor up to completion of the assigned CRT treatment (25 FD or 28 FD) (DLT period). A DLT must be confirmed by the SMC:

1. An adverse drug reaction that, in the opinion of the SMC, is of potential clinical significance such that further dose escalation would expose participants to unacceptable risk
2. Any occurrence of drug-induced liver injury (DILI) meeting the Hy's law criteria (i.e. defined as aminotransferases $> 3 \times$ ULN, alkaline phosphatase $< 2 \times$ ULN, total bilirubin $\geq 2 \times$ ULN, with no other reason to account for these abnormalities)
3. Any Grade 3 toxicity, excluding:
 - a) Diarrhea (< 7 days duration) despite early, adequate and optimal antidiarrhea therapy
 - b) Neutropenia lasting for ≤ 5 days and not associated with fever

- c) Isolated Grade 3 lymphocytopenia without clinical correlate
 - d) Grade 3 radiation dermatitis that resolves to Grade ≤ 2 with supportive measures within 5 weeks
 - e) Nausea and vomiting (< 3 days duration) with adequate and optimal therapy
 - f) Fatigue or headache (< 7 days duration) following initiation of adequate supportive care
 - g) Any other single laboratory values out of the normal range that have no clinical significance as confirmed by the Investigator, and that resolve to Grade 2 or less with adequate measures within 7 days
 - h) Grade 3 thrombocytopenia without bleeding
4. All Grade ≥ 4 AEs at least possibly related to study intervention, irrespective of duration, excluding:
- a) Isolated Grade 4 lymphocytopenia without clinical symptoms
 - b) Neutropenia lasting for ≤ 5 days and not associated with fever
5. Any toxicity related to study intervention that causes the participant to receive less than 80% of the planned peposertib, capecitabine or RT dose

[figure not shown]
6.6.2 Dosing Instructions

See [Table 7](#).

6.6.2.1 Peposertib

The participants will take peposertib orally once daily in the morning for 5 days a week (on all FDs) throughout the RT course in combination with capecitabine ([Figure 3](#)).

Figure 3 Dosing Schedule for Peposertib, Capecitabine, and Radiotherapy (28 Fraction Days^a)

PK=pharmacokinetic.

^aNote: In case of only 25 fraction days, treatment and radiotherapy will stop after 25 fraction days/5 weeks.

Peposertib tablets will be taken orally once daily in the morning, 1.5 h (± 30 min) prior to RT, for 5 days a week (on all FDs) throughout the RT course in combination with capecitabine. Peposertib must be taken after fasting for at least 1 h. Participants must continue fasting for 1 h after administration. The dose of peposertib in the starting cohort is 50 mg. The dose in subsequent cohorts will be determined by the SMC. No intraparticipant dose escalation is permitted.

If new data related to food effect and peposertib administration become available, the SMC may decide to recommend peposertib administration with food or to relax the food intake restriction.

Participants will take their assigned dose of peposertib once daily with a full glass of water (approximately 240 mL or 8 fluid ounces).

The participants will be instructed to swallow the tablets whole.

6.6.2.2 Capecitabine

Capecitabine is to be administered as recommended per current medical guidelines (NCCN 2019, Glynn-Jones 2017) for neoadjuvant treatment of locally advanced rectal cancer. The capecitabine dose is calculated according to body surface area.

Body surface area should be calculated based on established methods, e.g. the Mosteller formula (Mosteller 1987):

$$BSA (m^2) = \sqrt{\frac{Height (cm) \times Weight (kg)}{3600}}$$

Or in inches and pounds:

$$BSA (m^2) = \sqrt{\frac{Height (in) \times Weight (lbs)}{3131}}$$

If there is a change in body weight of at least 10% from baseline, the individual capecitabine doses should be recalculated. Otherwise the initial body surface area should be utilized for subsequent doses.

Capecitabine will be administered orally at a dose of 825 mg/m² twice daily 5 days a week throughout the RT course. The total daily dose, calculated in terms of mg/m², will be rounded to the nearest 500 mg, to allow for tablet size, and then divided into 2 doses. If this results in an uneven number of tablets (e.g. 7 tablets daily), then then the larger number will be taken with the morning dose (i.e. 4 tablets in the morning and 3 tablets in the evening). Capecitabine tablets are not to be split.

In addition, participants will be instructed to:

- Take capecitabine tablets in 2 daily doses: a morning dose and an evening dose
- Swallow capecitabine tablets with water within 30 min after a meal (breakfast and dinner).

6.6.2.3 Radiotherapy

Radiotherapy will be given at a total dose of 50 to 50.4 Gy to the tumor area and 45 Gy to the electively irradiated tissues in 25 or 28 fractions, concomitant integrated boost is allowed based on local guidelines (NCCN 2019, [Glynn-Jones 2017](#)). Radiotherapy will be given 5 days a week. Radiotherapy will be given using intensity modulated RT or volumetric modulated arc therapy, using gold standard for dose planning and rigorous constraints for organs at risk (OAR). Participants must be treated with fields that at least include the tumor, presacral nodes, mesorectal region, and internal iliac nodes. In addition, quality assurance on the delivered dose and fields will be mandated. Details are provided in [Appendix 4](#).

6.6.2.4 Administration of the Combination Therapy

The regimen for the study consists of once daily administration of peposertib together with capecitabine and RT:

- Capecitabine should be given within 30 min after a meal in 2 daily doses (a morning dose and an evening dose)
- Peposertib should be given 1 h after a meal
- Radiotherapy should be given 1.5 h (± 30 min) after peposertib dosing.

The combination therapy follows the SoC therapy schedule, which is generally administered over 25 or 28 FDs.

6.6.3 Management of Toxicities

Participants should be reviewed at least weekly during CRT when acute toxicity assessments are performed.

The following guidance should be followed for the management of acute toxicity and dose modifications:

- AEs should be graded according to the National Cancer Institute (NCI) Common Terminology Criteria for Adverse Events version 5.0 (CTCAE v5.0)
- In the event of overlapping toxicities, dose modification should be based on the worst toxicity grade observed.
- All dose modifications should be documented with clear reasoning and documentation of the approach taken in the case report and in the medical notes.
- If a participant experiences a toxicity, then dose modifications should be applied as per protocol, even if the toxicity has resolved by the time the participant is next seen.

6.6.3.1 Diarrhea

It is particularly important to assess and monitor participants who experience diarrhea during CRT. Recommendation for participants who experience diarrhea during concurrent CRT is given in the diarrhea management charter.

6.6.3.2 Capecitabine Management for Toxicities Other Than Diarrhea

Investigators must follow the package insert, the product information, the SmPC, and their site's specific policies/instructions for the final use of capecitabine.

Toxicity due to capecitabine administration may be managed by symptomatic treatment and/or modification of the dose (treatment interruption or dose reduction). Once the dose has been reduced, it should not be increased at a later time. For those toxicities considered by the treating physician to be unlikely to become serious or life-threatening, e.g. alopecia, altered taste, nail changes, treatment can be continued at the same dose without reduction or interruption. Participants taking capecitabine should be informed of the need to interrupt treatment immediately if moderate or severe toxicity occurs. Doses of capecitabine omitted for toxicity will not be replaced.

Hematological Toxicity

Participants with baseline neutrophil counts of $< 1.5 \times 10^9/L$ and/or platelet counts of $< 100 \times 10^9/L$ should not be treated with capecitabine. If these counts drop during treatment, doses of capecitabine are modified as shown in [Table 8](#).

Table 8 Dose Adjustment for Capecitabine for Absolute Neutrophil Count and/or Platelet Counts

Cell Count	Order of Occurrence	Action	Dose Resumed at (% of Starting Dose)
ANC $\geq 1.0 \times 10^9/L$ and platelets $\geq 75 \times 10^9/L$		Maintain capecitabine dose	100%
ANC $< 1.0 \times 10^9/L$ and/or platelets $< 75 \times 10^9/L$	First occurrence	Interrupt treatment until ANC $\geq 1.0 \times 10^9/L$ and platelets $\geq 75 \times 10^9/L$	100%
ANC $< 1.0 \times 10^9/L$ and/or platelets $< 75 \times 10^9/L$	Second occurrence	Interrupt treatment until ANC $\geq 1.0 \times 10^9/L$ and platelets $\geq 75 \times 10^9/L$	75%
ANC $< 1.0 \times 10^9/L$ and/or platelets $< 75 \times 10^9/L$	Third occurrence	Interrupt treatment until ANC $\geq 1.0 \times 10^9/L$ and platelets $\geq 75 \times 10^9/L$	50%
ANC $< 1.0 \times 10^9/L$ and/or platelets $< 75 \times 10^9/L$	Fourth occurrence	Discontinue capecitabine treatment	Not applicable

ANC=absolute neutrophil count.

Nonhematological Toxicity

For nonhematological toxicity due to capecitabine, doses are to be modified in line with [Table 9](#).

Table 9 Dose Adjustment for Capecitabine According to Common Terminology Criteria of Adverse Events Version 5.0 – Nonhematological Toxicity

Order of Occurrence	Grade 2	Grade 3	Grade 4
First Occurrence	Interrupt treatment until resolved to Grade 0/1, then continue at 100% or original capecitabine dose	Interrupt treatment until resolved to Grade 0/1, then continue at 75% or original capecitabine dose	Discontinue capecitabine treatment
Second Occurrence	Interrupt treatment until resolved to Grade 0/1, then continue at 75% or original capecitabine dose	Interrupt treatment until resolved to Grade 0/1, then continue at 50% or original capecitabine dose	
Third Occurrence	Interrupt treatment until resolved to Grade 0/1, then continue at 50% or original capecitabine dose	Discontinue capecitabine treatment	
Fourth Occurrence	Discontinue capecitabine treatment		

Source: EU Summary of Product Characteristics Version 02 February 2006.

6.6.3.3 Peposertib and Radiotherapy

The criteria for peposertib and RT dose modification in the study are included in [Table 10](#).

Table 10 Dose Modifications of Peposertib and Radiotherapy During the Study for toxicities other than Diarrhea

Toxicity	Dose Modifications	
	Peposertib ^a	Radiotherapy ^b
Toxicities in Radiation Field Grade 4		

 Radiation dermatitis. 	Temporarily interrupt peposertib. Resume treatment once severity resolves to Grade ≤ 3. Maximum delay of up to and including 7 days; otherwise permanently discontinue study intervention.	Temporarily interrupt treatment. Resume treatment once severity resolves to Grade ≤ 3 and dose distribution may be adjusted to spare skin.
Systemic Toxicities		
Hematologic Toxicities: Any Grade ≥ 3 toxicity, excluding: 
 Neutropenia lasting for ≤ 5 days and not associated with fever Isolated Grade 4 lymphocytopenia without clinical correlate Grade 3 thrombocytopenia without bleeding. 	Temporarily interrupt peposertib. Resume treatment (at the same dose) once severity resolves to Grade ≤ 1 or baseline. Maximum delay of 7 days; otherwise permanently discontinue peposertib. If there is a second recurrence at the same grade, permanently discontinue peposertib.	No action to be taken.
Nonhematologic Toxicities: Any Grade ≥ 3 toxicity, excluding: 
 Nausea and vomiting (< 3 days duration) with adequate and optimal therapy Fatigue or headache (< 7 days duration) following initiation of adequate supportive care Any other single laboratory values out of the normal range that have no clinical significance, and that resolve to Grade ≤ 2 with adequate measures within 7 days. Treatment-related hepatocellular damage for more than 3 days, such as Grade ≥ 3 ALT or AST with or without elevation of serum total bilirubin to > 2 × ULN, without initial findings of cholestasis (elevated serum alkaline phosphatase) or other apparent clinical causality.	Temporarily interrupt peposertib. Resume treatment (at the same dose) once severity resolves to Grade ≤ 1 or baseline. Maximum delay of 7 days; otherwise permanently discontinue study intervention. If there is a second recurrence, permanently discontinue peposertib. If Grade ≥ 3 liver enzyme values, the participant must be monitored at least every 4 days until recovery to Grade ≤ 2.	No action to be taken.

ALT=alanine aminotransferase, AST=aspartate aminotransferase, ULN=upper limit of normal.

- a As all treatments with peposertib will be given in combination with radiotherapy, an interruption in the administration of radiotherapy would lead to an interruption in treatment with peposertib.
- b A maximum radiotherapy delay of up to and including 7 days in total is allowed within the complete treatment period. If radiotherapy and peposertib treatment have to be delayed by more than 7 days, the participant must be discontinued from peposertib.

Severity of adverse events will be graded using the Common Terminology Criteria for Adverse Events (version 5.0) toxicity grades.

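### Table 10 exempts isolated Grade 4 but not isolated Grade 3 lymphocytopenia from peposertib interruption, so an event that Section 6.6.1 treats as not dose limiting can become a DLT or an exclusion through lost doses

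*Protocol*

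**What the plan says.** **Dosing rule.** In Protocol 6.6.3.3, Table 10, the hematologic row interrupts peposertib for Grade 3 or higher, with three exceptions: short afebrile neutropenia, Grade 3 thrombocytopenia without bleeding, and "Isolated Grade 4 lymphocytopenia without clinical correlate". Treatment resumes at the same dose on return to Grade 1 or baseline. Two limits apply: "Maximum delay of 7 days; otherwise permanently discontinue peposertib" and "If there is a second recurrence at the same grade, permanently discontinue peposertib". Radiotherapy continues unchanged. Under Section 6.6 a withheld study drug's "dose should be skipped rather than delayed", and physicians may depart from the dose-modification guidance.

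**DLT rule.** Section 6.6.1 removes "Isolated Grade 3 lymphocytopenia without clinical correlate" (3c) and "Isolated Grade 4 lymphocytopenia without clinical symptoms" (4a) from the DLT definition. Criterion 5 then adds: "Any toxicity related to study intervention that causes the participant to receive less than 80% of the planned peposertib, capecitabine or RT dose". The section also states: "A DLT must be confirmed by the SMC".

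**Analysis set.** The DE Analysis Set (Protocol 9.3, SAP 8.2) requires at least 80% of planned peposertib, except for participants who had a DLT.

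**Reporting.** SAP 15.1 plans a count of participants with an SMC-confirmed DLT by dose level, and a DLT listing whose columns are not specified. The adverse event listing in SAP 15.2.1 carries preferred term, grade, a yes/no DLT flag, relatedness and action taken with peposertib. SAP 10.1 lists the reason for peposertib termination.

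**The concern.** An exception that covers the more severe grade and not the milder one is the wrong way round. It looks like an omission. Table 10 carries over the other hematologic exceptions of 6.6.1 (3b and 4b for neutropenia, 4a for Grade 4 lymphocytopenia, 3h for thrombocytopenia), and only 3c is missing. No rationale is given. The event is foreseeable, since Section 2.3 names lymphoid depletion among the important potential risks.

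What is at stake is the primary endpoint, the number of participants with a confirmed DLT at each dose level, in cohorts planned at 3. If a DLT arose only because Table 10 withheld the drug for an event that 3c sets aside, the count would reflect the wording of a dosing table and not intolerance of the dose. If the SMC declined to confirm it, the participant would fall out of the denominator instead.

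**Working it through.** **1. The rules side by side**

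| Event (isolated, no clinical correlate) | DLT under 6.6.1, criterion 3 or 4? | Peposertib interrupted under Table 10? |
|---|---|---|
| Grade 3 lymphocytopenia | No (3c) | Yes |
| Grade 4 lymphocytopenia | No (4a) | No |

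**2. Doses that can be lost before criterion 5 applies**

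Inputs: 25 or 28 planned doses, one per fraction day; skipped doses are not made up (6.6); limit 80% (6.6.1 criterion 5, Protocol 9.3). Share received = (planned − skipped) / planned.

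| Skipped | 25-fraction schedule | 28-fraction schedule |
|---|---|---|
| 5 | 20/25 = 80.0% | 23/28 = 82.1% |
| 6 | 19/25 = 76.0% | 22/28 = 78.6% |

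Six skipped doses breach the limit on either schedule; five do not. A single interruption of 7 calendar days covers 5 fraction days and is therefore not enough.

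**3. Ways to reach six**

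- Permanent stop after failure to recover within 7 days. With no resumption, the first skipped dose must fall on or before FD20 of 25 (FD20 to FD25 is 6 doses) or FD23 of 28 (FD23 to FD28 is 6 doses).
- Two shorter interruptions that add up, for example 3 + 3 fraction days. Table 10 forces a permanent stop only at the second recurrence, so two interruptions can occur first.

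**4. What follows**

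If the event is related and the SMC confirms it, it is a criterion-5 DLT and the participant stays in the DE Analysis Set. If the SMC does not confirm it, exposure is below 80% and the participant is excluded.

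**5. What one such case could do in the escalation model (illustration)**

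Model from Protocol Appendix 10: logit P(DLT) = α + exp(β) × log(d/600), α ~ N(−0.847, variance 3.24), β ~ N(0.056, variance 0.64), zero covariance. Overdose risk is P(DLT rate > 0.33), capped at 25%. The pick minimizes the stated loss among allowed doses, with at most a doubling. The posterior was computed on a grid. The documents do not give results by cohort, so these are assumed.

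| Assumed data | Dose examined | Overdose risk | Model pick |
|---|---|---|---|
| 0/3 at 50, 0/3 at 100 mg | 200 mg | 4.1% | 200 mg |
| 0/3 at 50, 0/2 at 100 mg (one exclusion) | 200 mg | 5.4% | 200 mg |
| 0/3 at 50, 1/3 at 100 mg (one DLT) | 200 mg | 30.4% | 100 mg (150 mg if 150 and 250 mg are added to the dose set) |
| 0/3 at 50 and 100, 0/3 at 150 mg | 250 mg | 3.0% | 250 mg |
| 0/3 at 50 and 100, 1/3 at 150 mg (one DLT) | 250 mg | 21.3% | 250 mg |

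The last two rows use the dose set with 150 and 250 mg added, because the Synopsis reports doses from 50 to 250 mg and a 150 mg cohort. In these runs one extra DLT changes the pick at 100 mg but not at 150 mg, and the exclusion does not change it.

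**The case against.** The best reply has four parts.

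- **Different purposes.** Section 6.6.1 defines DLTs and Table 10 governs dosing. A dosing rule stricter than the DLT definition is not a contradiction. This stands. A reader might infer a direct conflict, but the documents show an inconsistency that matters only through criterion 5.
- **Discretion.** A sensible physician would read an exemption for Grade 4 as covering Grade 3, and 6.6 allows departures from the guidance. The SMC must confirm each DLT and may deviate from the model. This makes harm less likely but does not correct the rule. If the SMC declines to confirm, the result is an exclusion.
- **Traceability.** A reader might infer that the planned outputs hide the toxicity behind an exclusion, because the SAP 10.2.2 listing gives only an exposure or completion category. The documents do not support that. The adverse event listing shows preferred term, grade, DLT flag and action taken for each participant, and the peposertib-termination listing gives the reason. With 19 participants treated by 6 May 2021, cross-reference is easy. What no described output holds is the 6.6.1 criterion met. Even that is a limited statement, because the DLT listing's columns are unspecified and the separate SMC analysis plan is not among the documents reviewed.
- **No demonstrated case.** The route needs literal application, six lost doses, relatedness and an SMC decision. The model runs show what any single DLT does in a cohort of 3 and are not specific to lymphocytopenia. This stands, and it limits how far the point can be pressed.

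**Conclusion.** Table 10 is wrong as written: it interrupts peposertib for the milder event and not for the more severe one, out of line with 6.6.1. The consequence is conditional. A related isolated Grade 3 lymphocytopenia that costs six or more doses becomes a criterion-5 DLT if confirmed, or otherwise a DE-set exclusion, although 3c treats the event itself as not dose limiting.

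This rests on a literal reading of Table 10, on skipped doses not being made up, and on 7 days meaning calendar days. How often it happened cannot be computed from the documents. A reader might infer that the DLT counts or the MTD/RP2D conclusion were in fact distorted; nothing in the documents shows this. All participants have completed treatment and escalation has been stopped, so what remains is how DLTs and exclusions are interpreted and reported. For that purpose the correction should be made.

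**What to change.** 1. **Table 10.** Change the exception to: *Isolated Grade 3 or Grade 4 lymphocytopenia without clinical correlate*. The event would then cause no skipped doses and could not reach criterion 5. This is a protocol amendment that needs ethics approval, so include it in any further amendment. If none is planned, state the intended reading in the CSR.
2. **SAP 15.1.** Record in the DLT listing which 6.6.1 criterion each DLT met. The cost is one column.
3. **CSR.** If any criterion-5 DLT or DE-set exclusion rests only on isolated Grade 3 lymphocytopenia, say so beside the MTD/RP2D conclusion. The cost is one sentence, and the check may find no such case.

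No column for the causal preferred term is needed in either listing, because the event can already be traced. No second DLT count is needed.

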6.6.3.4 Radiotherapy Treatment Delay

Within this study, a maximum delay of up to and including 7 days in total is allowed within the complete Treatment period (Table 10). If RT and study intervention must be delayed by more than 7 days, the participant must be permanently discontinued from study intervention.

As all treatments with peposertib will be given in combination with RT, an interruption in the administration of RT would lead to an interruption in treatment with peposertib. Capecitabine can be continued or discontinued according to local guidelines.

If a participant misses RT administration, then the missed RT day will be made up (i.e. the missed RT dose is not skipped); participants should receive a total of 25 or 28 RT fractions.

